8.2.3. Adverse Event Summaries

An overall summary of AEs will include the following:

- Number (%) of participants reporting any TEAEs
- Number (%) of participants reporting any serious TEAEs
- Number (%) of participants reporting any Grade 3 or higher TEAEs

- Number (%) of participants reporting any TEAEs related to pemigatinib
- Number (%) of participants who temporarily interrupted pemigatinib because of TEAEs
- Number (%) of participants who permanently discontinued pemigatinib because of TEAEs
- Number (%) of participants with pemigatinib dose reductions because of TEAEs
- Number (%) of participants who had a fatal TEAE

The following summaries will be produced by MedDRA term:

- Summary of TEAEs by MedDRA SOC and PT
- Summary of TEAEs by MedDRA PT in decreasing order of frequency
- Summary of TEAEs by MedDRA SOC, PT, and maximum severity
- Summary of Grade 3 or higher TEAEs by MedDRA SOC and PT
- Summary of Grade 3 or higher TEAEs by MedDRA PT in decreasing order of frequency
- Summary of serious TEAEs by MedDRA SOC and PT
- Summary of serious TEAEs by MedDRA PT in decreasing order of frequency
- Summary of treatment-related TEAEs by MedDRA SOC and PT
- Summary of treatment-related TEAEs by MedDRA PT in decreasing order of frequency
- Summary of Grade 3 or higher treatment-related TEAEs by MedDRA SOC and PT
- Summary of treatment-related serious TEAEs by MedDRA SOC and PT
- Summary of TEAEs with a fatal outcome by MedDRA SOC and PT
- Summary of TEAEs leading to pemigatinib dose reduction by MedDRA SOC and PT
- Summary of TEAEs leading to pemigatinib dose interruption by MedDRA SOC and PT
- Summary of TEAEs leading to discontinuation of pemigatinib by MedDRA SOC and PT
- Summary of sponsor-defined clinically notable TEAEs by category and PT
- Summary of Grade 3 or higher sponsor-defined clinically notable TEAEs by category and PT
- Summary of serious sponsor-defined clinically notable TEAEs by category and PT
- Summary of sponsor-defined clinically notable TEAEs leading to dose reduction by category and PT

- Summary of sponsor-defined clinically notable TEAEs leading to dose interruption by category and PT
- Summary of sponsor-defined clinically notable TEAEs leading to discontinuation of study drug by category and PT

8.3. Clinical Laboratory Tests

8.3.1. Laboratory Value Definitions

Laboratory values and change from baseline values will be summarized descriptively by visit. Baseline will be determined according to Section 4.1.3. If there are multiple values that meet the criteria for baseline, additional rules may be provided after consultation with the medical monitor to delineate which value will be defined as baseline.

8.3.2. Laboratory Value Summaries

All test results and associated normal ranges will be converted to SI units. All tests with numeric values will have a unique unit per test.

Numeric laboratory values will be summarized descriptively in SI units, and non-numeric test values will be tabulated when necessary. In addition, line graph will be provided for phosphate, creatinine, blood urea nitrogen, calcium, sodium, 1,25-dihydroxyvitamin D, 25-hydroxyvitamin D, and parathyroid hormone.

Severity grades will be assigned to laboratory test values based on the numeric component of CTCAE v4.03. Shift tables will be presented showing change in CTCAE grade from baseline to worst grade postbaseline. Separate summaries for abnormally high and abnormally low laboratory values will be provided when the laboratory parameter has both high and low grading criteria. The denominator for the percentage calculation will be the number of participants in the baseline category. The number of participants who experienced worsening of laboratory abnormalities will be summarized by maximum severity.

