- Current evidence of clinically significant corneal disorder/keratopathy (including but not limited to bullous/band keratopathy, corneal abrasion, inflammation/ulceration, and keratoconjunctivitis, etc) or retinal disorder (including but not limited to macular/retinal degeneration, diabetic retinopathy, retinal detachment, etc) as confirmed by ophthalmologic examination.
- Use of any potent cytochrome P450 3A4 inhibitors or inducers within 14 days or 5 half-lives (whichever is shorter) before the first dose of study drug.

Pemigatinib, Dosage, and Mode of Administration:

Pemigatinib will be self-administered as a QD oral treatment on a 2-weeks-on-therapy and 1-week-off-therapy schedule or continuous administration (no planned dose hold). Each dose of pemigatinib should be taken as soon as possible after rising with or without food. Tablets will be available in strengths of █ mg and 4.5 mg. The starting dose will be 13.5 mg. One cycle will be defined as 21 days of treatment.

Reference Therapy, Dosage, and Mode of Administration:

Not applicable.

Study Schedule/Procedures:

Subjects will have regularly scheduled study visits at the clinical site as part of a 21-day cycle. Study visits are as follows:

- Screening: Day -28 through Day -1
- Cycle 1: Days 1, 8, and 15 (\pm 3 days)
- Cycles 2+: Day 1 (\pm 3 days) of each cycle or Day 1 (\pm 3 days) of every third cycle (with telemedicine visits conducted in between) when subject has reached the long-term treatment visit schedule (after completing Cycle 18).
- End of treatment (EOT): Upon permanently discontinuing study drug
- Safety follow-up: 30 days (+ 5 days) from date of last dose
- Disease status: Follow subject per standard of care until documented progression
- Survival follow-up: Every 12 (+2) weeks

Laboratory Tests:

Study visits will include sample collection for chemistry, hematology, coagulation, lipid panel, endocrine monitoring, and urinalysis testing. As of Protocol Amendment 6, lipid panel will only be analyzed at Cycle 1 Day 1. Additionally, hepatitis screening (serology) will be done at screening, and pregnancy testing will be done at screening, Day 1 of every cycle before dose administration, and EOT. Subjects who underwent hematopoietic stem cell transplant during the study will continue to have hematology blood tests done concomitantly with the bone marrow assessments.

Central Laboratory:

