5.2. Study Drug

5.2.1. Pemigatinib

5.2.1.1. Description and Administration

Pemigatinib will be self-administered as a QD oral treatment on a 21-day cycle. Subjects will take study drug for 2 weeks continuously (14 days) followed by a 1-week (7 days) break. The starting dose will be 13.5 mg. With Protocol Amendment 3, the administration schedule was adjusted, and newly enrolled subjects will receive pemigatinib at 13.5 mg continuous administration (no planned dose hold). Subjects receiving treatment under previous versions of the Protocol may be switched to continuous administration after completing at least 3 cycles if there are no ongoing Grade 2 or higher related TEAEs. The written request to switch to continuous administration should be sent to the sponsor's medical monitor.

Based on results from the food effect cohort in Study INCB 54828-101, pemigatinib may be administered with or without food.

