5.4.4. Up-Titration

Any subject treated at 13.5 mg QD will be titrated up to 18 mg QD using their current dose regimen with approval from the medical monitor if the subject meets the following criteria:

- Has been on study drug for at least 1 cycle.
- Has been compliant with taking study drug.
- Has no ongoing Grade 2 or higher treatment-related AE.
- Has not had hyperphosphatemia, defined as a serum phosphate level of > 5.5 mg/dL.

Subjects who are titrated up to 18 mg QD will begin the next cycle at the new dose level and must agree to all Cycle 1 assessments (PK and safety assessments [hematology and blood chemistry]). Up-titration may occur no earlier than Cycle 2 Day 1, so that subjects are observed for phosphate level and AEs for at least 1 cycle.

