Bone marrow examination (core biopsy and aspiration)	7.6, 7.9.4	X*				X**	X		X***		*Within 6 weeks before enrollment. **See Section 7.6 for assessment frequency. ***In subjects who do not discontinue due to progressive disease, including subjects in post-transplant follow-up.	
Lymph node/EMD biopsy (optional)	7.6	X*				X*					*In subjects who present with lymphadenopathy or other EMD, biopsy is recommended at baseline and at the time of progression.	
Cytogenetic analysis	7.6	X				X*	X		X**		*See Section 7.6 for assessment frequency. **In subjects who do not discontinue due to progressive disease, including subjects in post-transplant follow-up.	
EMD assessment by PET-CT or CT scan	7.6	X			X*	X*	X*		X*		See Section 7.6 for assessment frequency. *If baseline assessment is positive for EMD.	
Survival status	6.4.3									X		

CT = computed tomography; PET = positron emission tomography.

Table 5: Laboratory Assessments

	Protocol Section	Screening	Treatment				EOT	Safety Follow-Up 30 days from EOT (+5 days)	Notes			
			Cycle 1									
			Day 1	Day 8 (± 3 Days)	Day 15 (± 3 Days)							
LOCAL LABORATORY												
Serum chemistries	7.5.6	X	X*	X	X	X**	X	X	*May be performed within 3 days of the first dose. **Assess for up-titration (Section 5.4.4).			
Hematology	7.5.6	X	X*	X	X	X	X	X**	*May be performed within 3 days of the first dose. **Including subjects in post-transplant follow-up.			
Lipid panel	7.5.6		X									
Endocrine	7.5.6	X	X			X	X					
Coagulation panel	7.5.6	X				X*	X		*Every 3 cycles starting with Cycle 3.			
Hepatitis screening	7.5.6.2	X										
Urinalysis	7.5.6	X				X*			*Every 3 cycles starting with Cycle 3			
Pregnancy test	7.5.6.1	X (Serum)	X*			X*	X*		*Urine pregnancy test allowed; Day 1 of each cycle (see Section 6.2.1 for long-term treatment details).			

Table 5: Laboratory Assessments (Continued)

Protocol Section	Screening	Treatment				Cycles 2+ EOT	Safety Follow-Up 30 days from EOT (+5 days)	Notes			
		Cycle 1									
		Day 1	Day 8 (± 3 Days)	Day 15 (± 3 Days)							
CENTRAL LABORATORY											
Bone marrow (aspirate, core, and peripheral blood smear)	7.6, 7.9.4	X				X*	X	*See Table 7 for assessment frequency.			
PK	7.8		X	X				Samples will be drawn at predose and 1, 2, and 4-12 hours postdose (4 samples total on each day).			
Correlative plasma sample	7.9.3		X		X	X*		*C2D1, C4D1, C8D1, then at the times of scheduled bone marrow sampling (see Table 7 for assessment frequency).			

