6.2.1. Long-Term Treatment Visit Schedule

After completion of the Cycle 18 Day 1 (51 weeks on study treatment) visit, the frequency of study visits conducted at the investigative site may be extended to every 3 cycles (9 weeks) if the following criteria are met and the study site receives medical monitor approval:

- The subject has no ongoing \geq Grade 3 TEAEs or \geq Grade 2 treatment-related TEAEs.
- The subject has maintained an overall response of PR or better for at least 3 consecutive assessments.
- The subject has maintained a CCyR for at least 3 consecutive assessments.

- Women of childbearing potential must agree to have monthly pregnancy testing performed at home or at a local laboratory and must immediately notify the study site of a positive result so study medication can be held while a serum pregnancy test is performed. Urine pregnancy test kits may be provided to subjects.

In the interval between visits to the study site, sites must conduct remote/telemedicine visits with the subjects on Day 1 of each cycle (\pm normal visit window) to assess AEs, concomitant medications, ECOG performance status, and study medication compliance. Likewise, subjects must complete the scheduled laboratory assessments at a laboratory convenient to their homes. Data from these remote/telemedicine visits as well as the laboratory data collected will be entered into the eCRF at their respective cycle visits.

Subjects who may be eligible to switch to this long-term treatment visit schedule but have already surpassed Cycle 18 at the time of Protocol Amendment 6 may begin following this schedule in conjunction with a cycle that has the same assessments as Cycle 18 (eg, in conjunction with an eye exam), if the above criteria are satisfied.

Subjects may revert back to attending every study visit at the investigative site as needed (eg, to manage a new or worsening adverse event) but must always resume the extended investigative site visit schedule in conjunction with a cycle that has the same assessments as Cycle 18.

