4.1.5. Cycle Length and Duration

Cycle 1 Day 1 is the day that the first dose of study drug is administered. Scheduled cycle length is 21 days with first day of each cycle corresponding with the first day of pemigatinib administration in that cycle.

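### From Cycle 2 on, routine phosphate samples follow the off week in intermittent subjects but follow a dose in continuous subjects, and the SAP pools both under one nominal visit

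*SAP*

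**What the plan says.** **Dosing.** Protocol 5.2.1.1 describes the intermittent schedule: "Subjects will take study drug for 2 weeks continuously (14 days) followed by a 1-week (7 days) break". Subjects newly enrolled under Amendment 3 or later receive the drug continuously. Earlier subjects may switch after at least 3 cycles if they have no ongoing related event of Grade 2 or higher.

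**Sampling.** Protocol Table 5 schedules serum chemistry at screening, on Cycle 1 Days 1, 8 and 15, at the Cycle 2+ visits, at end of treatment and at safety follow-up. Table 6 places phosphate, calcium and both vitamin D assays in that panel. The synopsis puts the Cycle 2+ visits on Day 1, within 3 days either way. Parathyroid hormone is in the separate endocrine row, which has no Day 8 or Day 15 draw.

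**Cycle Day 1.** SAP 4.1.5 defines it, with the "first day of each cycle corresponding with the first day of pemigatinib administration in that cycle".

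**Analysis.** SAP 8.3.1 summarizes laboratory values and changes from baseline by visit. SAP 4.1.6 takes the visit as recorded on the eCRF, without windowing. SAP 5.2 reports one total column. SAP 8.3.2 adds: "line graph will be provided for phosphate, creatinine, blood urea nitrogen, calcium, sodium, 1,25-dihydroxyvitamin D, 25-hydroxyvitamin D, and parathyroid hormone". SAP Appendix C titles this figure as selected laboratory values by study visit.

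**The concern.** Protocol 1.3.2.1 says the rise in serum phosphate depends on exposure and calls hyperphosphatemia an expected on-target effect. A phosphate curve is thus partly a curve of drug exposure at the time of sampling.

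Under one label, such as Cycle 3 Day 1, the plan combines samples taken about a day after a dose with samples taken after a week's break. A reader of the pooled graph could see phosphate settle after Cycle 1 and conclude that the effect had resolved or was under control, when part of the change came from the day of sampling. As intermittent subjects switch to continuous dosing, the mean could rise again for the same reason. The switchers are also selected, since ongoing related events of Grade 2 or higher rule out a switch.

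What is at stake is the reading of a descriptive safety display. No efficacy result depends on it.

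**Working it through.** **Inputs**
- Intermittent doses on Days 1 to 14 of a 21-day cycle (Protocol 5.2.1.1).
- Cycle 2+ draws on Day 1, window 3 days either way (Protocol synopsis, Table 5).
- Mean half-life 18.8 h (Protocol 1.3.2.1).
- Assumptions: pre-dose draws, doses taken 24 h apart, and residual drug = 0.5^(hours since last dose / 18.8), ignoring accumulation.

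**1. Check of the calendar against a stated figure.** Protocol 6.2.1 gives a date for Cycle 18: "After completion of the Cycle 18 Day 1 (51 weeks on study treatment) visit". With 21-day cycles, (18 − 1) × 21 / 7 = 51.0 weeks. The figure reproduces, so Day 1 visits do fall 21 days apart.

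**2. Time since last dose, intermittent schedule.** Cycle 2 Day 1 is study day 22 and the last dose is on day 14.
- Nominal Day 1: (22 − 14) × 24 = 192 h; 192 / 18.8 = 10.2 half-lives; 0.5^10.2 = 0.08% left.
- Three days early (day 19): (19 − 14) × 24 = 120 h; 6.4 half-lives; 1.2% left.
- One to three days late with dosing restarted on Day 1: about 24 h after a dose, so on drug.
- Cycle 1 Days 8 and 15, nominal: 24 h each; 1.3 half-lives; 41% left.

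**3. Same visit, continuous schedule.** A pre-dose Day 1 draw is about 24 h after the previous dose, which is 41% by the same formula. This matches Cycle 1 Days 8 and 15 on either schedule. The two schedules therefore agree in sampling time during Cycle 1 and diverge from Cycle 2.

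**4. How many draws are affected.** For a subject who stays intermittent, the nominal postbaseline in-treatment draws through Cycle 18 Day 1 are 2 in Cycle 1 (Days 8 and 15) plus 17 Day 1 draws, 19 in all. Of these, 17 follow the break. End of treatment and safety follow-up are not counted.

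**5. Effect on the pooled mean.** Let f be the share of intermittent subjects at a visit. Suppose both groups have the same on-drug rise and intermittent subjects keep a fraction r of it on Day 1. The pooled rise is then (1 − f) + f × r of the continuous-schedule rise. With full recovery (r = 0) it is 1 − f: 90% at f = 0.1, 70% at f = 0.3, 50% at f = 0.5. With no recovery (r = 1) there is no distortion. A fall in f from 0.3 to 0.1 through switching would lift the r = 0 curve from 70% to 90% with no change in anyone's on-drug phosphate. The documents give neither f nor r, so this is a range and not an estimate.

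**6. Other planned summaries.** SAP 8.3.2 plans shifts to the worst postbaseline CTCAE v4.03 grade. The documents do not say whether that version grades high phosphate. Protocol 9.4.2.2 also plans a low/normal/high shift to the worst value for parameters without a CTCAE grade. Neither SAP 8.3.2 nor the table titles in SAP Appendix C repeat it, although SAP 9.1 lists no such change. No summary of maximum phosphate is named.

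**The case against.** The strongest reply is that hyperphosphatemia on the intermittent schedule is detected by several routes outside the Day 1 draws:
- Cycle 1 Days 8 and 15 are themselves by-visit points close to a dose.
- Abnormal phosphate brings monitoring at least twice a week (Protocol Tables 2 and 3), and assessments at unscheduled visits go into the eCRF (6.6).
- Up-titrated subjects repeat the Cycle 1 chemistry in a later cycle (5.4.4).
- Hyperphosphatemia events are tabulated (Protocol 9.4.2.1; SAP 8.2.2), and abnormal chemistry values are listed.
- Protocol Table 1 reports the event in 230 of 438 intermittent subjects (52.5%) in the pooled studies.

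This stands against four stronger readings that a reader might infer.
- *No on-drug rise could be detected.* The routes above rule this out.
- *All samples after Cycle 1 are off drug.* End-of-treatment draws, repeated Cycle 1 chemistry and late Day 1 draws need not follow the break.
- *Phosphate must be back to normal on Day 1.* The half-life shows drug washout, but the documents give no recovery time for phosphate, calcium, vitamin D or parathyroid hormone.
- *Table 1 shows an off-week rebound.* Hyperphosphatemia was 52.5% intermittent against 74.1% continuous, and hypophosphatemia 15.3% against 8.2%. These are adverse event terms from nonrandomized studies without sampling times, so other differences between the groups could explain them.

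Nor do the up-titration rule and Table 5 conflict. The criterion in 5.4.4, "Has not had hyperphosphatemia, defined as a serum phosphate level of > 5.5 mg/dL", covers any value to date. The section also requires observation for at least one cycle, which includes the Day 8 and Day 15 draws.

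The reply does not rescue the by-visit displays. Twice-weekly monitoring starts only after an abnormal value, so an on-drug rise that first occurs after Cycle 1 and settles during the break may leave no trace in routine samples. The SAP also gives no rule that places unscheduled values in the nominal-visit graph.

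**Conclusion.** The concern holds in a limited form. After Cycle 1, the planned by-visit phosphate summaries and line graph mix two sampling times: about 8 days after the last dose (192 h, 10.2 half-lives, about 0.1% of drug left) on the intermittent schedule, and about 1 day on the continuous schedule. Nothing in the SAP separates or labels them. The pooled curve can understate on-drug phosphate and can shift as subjects change schedule. Calcium and vitamin D, drawn in the same panel, share the timing problem. Parathyroid hormone does too, but it has no Day 8 or Day 15 value from which a fall could be seen.

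The timing rests on the documents' own schedule and half-life, with nominal pre-dose draws. The direction of the phosphate effect rests on the Protocol's statement that the rise depends on exposure. The size cannot be computed: it lies between no distortion and a loss equal to the intermittent share of subjects, on the equal-rise assumption above. This is a worthwhile, inexpensive improvement to a descriptive safety display. It does not show that hyperphosphatemia goes undetected overall.

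**What to change.** In SAP 8.3.2:
1. Present the by-visit summaries and line graphs for phosphate, calcium and vitamin D separately by the dosing schedule in force at the visit. Count a switching subject's first Day 1 draw with the cycle just completed, because it follows that cycle's break.
2. Label Cycle 2+ Day 1 values in intermittent subjects as post-break. Use days since last dose where the recorded dosing dates allow. SAP 6.5 mentions a Dosing CRF but the documents do not show its fields, so this needs checking. The schedule split alone is not enough, since an intermittent-only curve after Cycle 1 is still mostly post-break values. A fixed cutoff in days is not needed.
3. Label parathyroid hormone values in the same way, but do not restrict them to on-drug samples. With no Day 8 or Day 15 draw, intermittent subjects would have almost no postbaseline values left.
4. Add a summary of maximum postbaseline phosphate, including unscheduled values, with the number and percentage above 5.5 mg/dL, the Protocol's own definition of hyperphosphatemia.
5. Carry over from Protocol 9.4.2.2 the low/normal/high shift to the worst value for parameters without a CTCAE grade, and add it to Appendix C.

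The cost is SAP text, a derived schedule or post-break flag and minor programming, with no new blood draws. The drawback is fewer subjects per curve, in a study planned for about 46. The maximum summary will recover unscheduled peaks, but not an on-drug rise that was never sampled.

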8.3.3. Potential Hy's Law Events

The participants with elevated alanine aminotransferase or alanine aminotransferase $> 3 \times$ upper limit of normal range and alkaline phosphatase $< 2 \times$ upper limit of normal range accompanied by total bilirubin $> 2 \times$ upper limit of normal range at the same visit will be listed.

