5.4.2. Criteria and Procedures for Dose Interruptions and Adjustments of Study Drug

Safety concerns should be discussed with the sponsor immediately upon occurrence or awareness to determine whether the subject should continue or discontinue study treatment. For subjects who present with possible or confirmed serous retinal detachment/retinal pigmented epithelium detachment (SRD/RPED) based on optical coherence tomography (OCT), the guidelines in [Table 2](#) should be followed. It is recommended to discuss the findings with the Incyte medical monitor before making changes to the subject's treatment.

Per CTCAE v 4.03, there is a grading for retinal detachment, however, this refers to rhegmatogenous retinal detachment (when a hole occurs in the retina) or exudative detachment (fluid accumulation due to inflammatory diseases). There is no exact CTCAE grading term for SRD/RPED secondary to FGFR inhibition (there is no hole in the macula, just fluid accumulation or detachment of retinal pigmented epithelium). Therefore, grading should be based on the CTCAE term "retinopathy."

Treatment with pemigatinib may be delayed up to 14 days to allow for resolution of toxicity. Subjects may resume treatment if no medical condition or other circumstance exists that, in the opinion of the investigator, would make the subject unsuitable for further participation in the study. The treating investigator should contact the sponsor to discuss the case of any subject whose treatment has been delayed for more than 14 days before restarting treatment with pemigatinib.

Table 2: Guidelines for Interruption and Restarting of Study Drug

Toxicity/CTCAE Grade	Action Taken	
Chemistry		

 AST and/or ALT is $> 5.0 \times \text{ULN}$. ALP $> 5 \times \text{ULN}$. 
Note: In subjects with bone metastasis-related elevations at baseline, contact sponsor to discuss clinical management and possible dose reductions.
	
Step 1: Interrupt study drug up to 2 weeks (14 days) until the toxicity has resolved to \leq Grade 1 except by approval of the medical monitor.
 
Step 2: If assessed as related to study drug, restart study drug at next lower dose; monitor as clinically indicated.
	
Hy's law: ALT $> 3.0 \times \text{ULN}$, ALP $< 2 \times \text{ULN}$, and bilirubin $\geq 2.0 \times \text{ULN}$; no evidence of biliary obstruction or other causes that can reasonably explain the concurrent elevation.	Discontinue treatment.	
Hematology		

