2.1 Discontinued Participants (Participant Disposition)	
2.1.1	Participant Enrollment and Disposition Status
2.1.2	Participant Inclusion and Exclusion Criteria Violations
2.2.1	Protocol Deviations
2.3.1	Analysis Population
2.4.1	Demographic and Baseline Characteristics

Listing No.	Title
2.4.2	Disease Characteristics
2.4.3	Prior Systemic Therapy
2.4.4	Prior Radiotherapy
2.4.5	Prior Surgery or Surgical Procedure
2.4.6	Prior Stem Cell Transplant
2.4.7	Medical History
2.4.8	Prior and Concomitant Medication
2.4.9	Procedure and Non-drug Therapy
2.4.10	Post Therapy
2.5.1	Study Drug Compliance
2.5.2	Study Drug Administration
2.6.1	Response Criteria for Myeloid/Lymphoid Neoplasms - Investigator
2.6.2	Response Criteria for Myeloid/Lymphoid Neoplasms - Central Review
2.6.3	Bone Marrow
2.6.4	Flow Cytometry
2.6.5	Response Assessment: Target Lesions
2.6.6	Response Assessment: Non-target Lesions
2.6.7	Response Assessment: New Lesions
2.6.8	Investigator Response Criteria for Extramedullary Disease
2.6.9	Results of Central Histopathology Review
2.6.10	Spleen and Liver Examination
2.6.12	5 Point Scale
2.6.15	Stem Cell Transplant
2.7.1	Adverse Events
2.7.2	Serious Adverse Events
2.7.3	Grade 3 and Higher Adverse Events
2.7.4	Fatal Adverse Events
2.7.5	Treatment-Related Adverse Events
2.7.6	Adverse Events Leading to Interruption, Reduction, or Discontinuation of Pemigatinib
2.7.7	Sponsor-Defined Clinically Notable Adverse Events
2.8.1	Clinical Laboratory Values – Hematology
2.8.2	Clinical Laboratory Values – Chemistry
2.8.3	Clinical Laboratory Values – Coagulation
2.8.4	Clinical Laboratory Values – Urinalysis
2.8.5	Abnormal Clinical Laboratory Values– Hematology
2.8.6	Abnormal Clinical Laboratory Values– Chemistry
2.8.7	Potential Hy's Law Events
2.8.8	PK Blood Sampling Times
2.9.1	Vital Signs
2.9.2	Abnormal Vital Sign Values
2.9.3	Alert Vital Sign Values
2.10.1	12-Lead ECG Values
2.10.2	Abnormal 12-Lead ECG Values
2.10.3	Alert 12-Lead ECG Values
2.11.1	Eye Examination

Listing No.	Title
2.11.2	Fundus Photography
2.11.3	Optical coherence tomography
2.11.4	ECOG Performance Score
2.11.5	PRBC/Platelet Transfusions

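### The SAP's Hy's law rule names ALT twice and omits AST, and its bilirubin cut-off excludes the boundary value that Protocol Table 2 includes

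*SAP*

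**What the plan says.** SAP 8.3.3 defines who appears in Listing 2.8.7, "Potential Hy's Law Events". Its aminotransferase criterion begins "The participants with elevated alanine aminotransferase or alanine aminotransferase" and sets a limit of > 3 × ULN. It adds ALP < 2 × ULN and total bilirubin > 2 × ULN, and closes with "upper limit of normal range at the same visit will be listed". AST is not named anywhere in the rule.

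The Hy's law row of Protocol Table 2 (Section 5.4.2) requires ALT > 3.0 × ULN, ALP < 2 × ULN and bilirubin ≥ 2.0 × ULN, with "no evidence of biliary obstruction or other causes that can reasonably explain the concurrent elevation". It attaches a treatment-discontinuation instruction. This row does not name AST either. The first chemistry row of the same table does take the two enzymes together ("AST and/or ALT is").

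SAP 9.1 declares one departure from the Protocol's analyses, the change to the efficacy evaluable population. It does not mention the Hy's law rule. SAP Table 6 shows a single version of the plan, and SAP 2.1 keeps that version in force for later Protocol amendments unless it is superseded.

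**The concern.** The duplicated analyte shows that the author meant to name two enzymes. A programmer who follows the text will code ALT alone, and a participant whose rise is in AST only will not be selected, with nothing in the output to show the gap. Separately, the Protocol and the SAP disagree on whether a bilirubin of exactly twice the ULN counts, and nothing marks the difference as deliberate.

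At stake is the completeness of the one planned output that puts the aminotransferase, ALP and bilirubin criteria together. The liver signal is not hypothetical. Protocol 1.3.1 reports reversible ALT and AST rises in monkeys. Protocol 1.3.2 reports, in this study, one related serious event of hypertransaminasemia and one discontinuation for raised ALP. Protocol 8.7 plans no independent data monitoring committee. A screening listing for this signal should capture at least what the Protocol's own laboratory thresholds capture.

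**Working it through.** The plan gives no figure to reproduce, so the check sets the two rules side by side and then tests them as logical conditions.

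| Element | SAP 8.3.3 | Protocol Table 2, Hy's law row |
|---|---|---|
| Aminotransferase | ALT (named twice) > 3 × ULN | ALT > 3.0 × ULN |
| ALP | < 2 × ULN | < 2 × ULN |
| Bilirubin | > 2 × ULN | ≥ 2.0 × ULN |
| Timing | same visit | concurrent, with no visit condition |
| Other causes | not mentioned | must be absent |

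**Laboratory conditions, in multiples of ULN**

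- Protocol: ALT > 3 and ALP < 2 and bilirubin ≥ 2.
- SAP as written: (ALT > 3 or ALT > 3) and ALP < 2 and bilirubin > 2. The bracket reduces to ALT > 3.
- Comparison rule, with the second ALT read as AST and the bilirubin boundary matched to Table 2 as it stands: (ALT > 3 or AST > 3) and ALP < 2 and bilirubin ≥ 2.

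**Test profiles (ALT, AST, ALP, bilirubin)**

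| Profile | Protocol | SAP as written | Comparison rule |
|---|---|---|---|
| 4, 4, 1, 2.0 | met | not listed | listed |
| 4, 4, 1, 2.05 | met | listed | listed |
| 4, 1, 1, 3 | met | listed | listed |
| 2, 5, 1, 3 | not met | not listed | listed |
| 2, 5, 1, 2.0 | not met | not listed | listed |
| 3, 3, 1, 3 | not met | not listed | not listed |

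**Loss against the Protocol.** ALT and bilirubin were each run from 0.5 to 6.0 in steps of 0.1, with ALP at 1. The SAP rule misses 30 grid points that meet the Protocol thresholds. All 30 have bilirubin exactly 2.0, one for each ALT value from 3.1 to 6.0: (6.0 − 3.1)/0.1 + 1 = 30. In practice this is a single laboratory value. With an assumed ULN of 17, 20, 21 or 22 µmol/L and integer results, it is 34, 40, 42 or 44 µmol/L respectively.

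**Loss from omitting AST.** With bilirubin at 3, no combination of ALT and AST on the grid meets the Protocol's conditions and escapes the SAP's. The AST-only profile (2, 5, 1, 3) fails both. It is lost only relative to a rule that names AST.

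**Timing and other causes.** These cannot be tested on a grid. The same-visit condition could make the SAP narrower if two results from different visits would be judged concurrent under Table 2. Leaving out the other-causes condition makes the SAP broader, which is reasonable for a listing of potential events.

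**The case against.** The strongest reply is that almost nothing is lost. A reader might infer from the duplicated ALT that the Protocol includes AST and the SAP dropped it, so that cases qualifying under the Protocol disappear. The documents do not support that: Table 2's Hy's law row is ALT-only, and the AST omission loses no case that meets it. That AST was meant is an inference. It rests on the otherwise idle or and on the pairing of the two enzymes in exclusion criterion 5b, the first chemistry row of Table 2 and Protocol 1.3.1. Neither document states it. Against the Protocol's numerical thresholds, the loss is one boundary value.

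A reader might also infer that this is the only place liver injury would show. It is the only combined-criteria display, but AST, ALT, ALP and bilirubin are all required analytes in Protocol Table 6. They would also appear in Listing 2.8.2 ("Clinical Laboratory Values – Chemistry"), abnormal values in Listing 2.8.6, and grade shifts and worsening in Tables 3.3.3.2 and 3.3.3.5. Finally, nothing in the documents routes Table 2 decisions through Listing 2.8.7. The listing belongs to the Clinical Study Report (SAP Appendix C), so neither treatment nor the primary analysis is affected.

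All of this stands, and it limits the size of the point. It does not make the rule correct as written. The shift and worsening tables take each parameter separately and do not show concurrent elevation. In the general listings a reader would have to find the combination by hand.

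**Conclusion.** Two drafting faults are confirmed on the page: SAP 8.3.3 duplicates ALT where a second enzyme belongs, and its bilirubin operator differs from Table 2's without explanation. The listing could therefore omit AST-only cases that the SAP evidently meant to show. It would omit a case that meets the Protocol's laboratory thresholds with bilirubin at exactly 2.0 × ULN, should one occur. The same-visit condition may narrow it further.

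The size is small. Few such cases are to be expected, and one descriptive safety listing is involved. The conclusion rests on reading the second ALT as a slip for AST and on the listing being programmed literally. If the programmer silently substituted AST, only the bilirubin boundary and the visit condition would remain. The change is worth making because a safety screen should not depend on such a substitution, and the correction is nearly free.

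**What to change.** In SAP 8.3.3, correct the duplicated analyte so that the listing screens on ALT or AST. Reconcile the bilirubin operator and the same-visit condition with Protocol Table 2, so that the listing captures at least every participant who meets the Protocol's laboratory thresholds, and say so in the text. If results from different visits can count as concurrent, state the rule for pairing them. Record the change in SAP 9.2.

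This concerns the analysis listing only. The Protocol's rule for stopping treatment is not changed by it. Whether the SAP and Table 2 should name the same analytes and boundary is for the sponsor to reconcile. The cost is one SAP sentence and a small change to the code for Listing 2.8.7. No new data are needed, because all the analytes are already required by Protocol Table 6.
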